2.2 Secondary objectives

Key Secondary Objectives

- To evaluate everolimus with reduced exposure CNI compared to MPA plus standard exposure CNI at 12 months post-transplantation with respect to the composite efficacy failure rate of (treated biopsy proven acute rejection (tBPAR), graft loss or death).
- To evaluate the binary composite endpoint of tBPAR or eGFR < 50 mL/min/1.73m² (MDRD4) Month 12 among compliant subjects.

Other Secondary Objectives

To evaluate, by treatment group;

- The incidence of composite endpoint of tBPAR or eGFR < 50 mL/min/1.73m² (MDRD4) at Month 24.
- The incidence of composite endpoint of tBPAR (excluding Banff grade 1A acute rejections) or eGFR < 50 mL/min/1.73m² (MDRD4) at Month 24.
- The incidence of composite endpoint of tBPAR or eGFR < 50 mL/min/1.73m² (MDRD4) at Month 12 by subgroup (see Section 9.4.4).

- The incidence of composite endpoint of tBPAR, graft loss or death at Month 24.
- The incidence of composite endpoint of tBPAR, graft loss, death, or loss to follow-up at Months 12 and 24.
- The incidence of composite endpoint of tBPAR, graft loss, death or eGFR < 50 mL/min/1.73m² at Months 12 and 24.
- The incidence of composite endpoint of graft loss or death at Month 12 and 24.
- The incidence of individual endpoints of death, graft loss, tBPAR, BPAR, tAR, AR and humoral rejection at Months 12 and 24.
- The incidence of tBPAR by severity and time to event.
- The incidence of tBPAR excluding Banff 1A grade acute rejections
- The incidence of transplant recipients with eGFR < 50 mL/min/1.73m² at Months 12 and 24.
- Renal allograft function and change in renal allograft function from Month 1 (eGFR) at Months 12 and 24.
- The evolution of renal function, as eGFR, over time by slope analysis.
- Renal function by Cystatin C-based and other alternate formulae (e.g. CKD-EPI).
- The incidence of adverse events, serious adverse events and adverse events leading to study regimen discontinuation.
- The incidence of CMV and BKV, new onset diabetes mellitus, chronic kidney disease with associated proteinuria and CNI associated adverse events.
- Urinary protein and albumin excretion by treatment estimated by urinary protein/creatinine and urinary albumin/creatinine ratios.
- The incidence of major cardiovascular events.
- The incidence of malignancies.

3 Investigational plan

[figure not shown]

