9.4.4 Supportive analyses

The following analyses will serve as supportive analyses for the primary endpoint of tBPAR or eGFR (MDRD4)<50 mL/min/1.73m² at Month 12.

The analysis outlined for the primary endpoint in Section 9.4.2 will be repeated using compliant subjects in the FAS population.

Analysis on Per-Protocol Set

The analysis outlined for the primary endpoint in Section 9.4.2 will be repeated using the Per-Protocol Set.

Subgroup analysis

Subgroup analyses will be done for the primary composite endpoint of tBPAR or eGFR (MDRD4)<50 mL/min/1.73m² at 12 months for the subgroups defined by:

- recipient characteristics (recipient age group: <60 vs ≥60 yr, gender, race, region)
- donor/transplant characteristics (donor age group: <60 vs ≥60 yr, gender, cold ischemia time: < 20 vs ≥20 hr, end stage disease leading to transplant, donor type; living donor, standard criteria deceased donor and expanded criteria deceased donor; HLA mismatches: <=3 vs >3)
- CNI (tacrolimus vs. cyclosporine)
- Induction (basiliximab vs. rATG)
- Immunological risk (high vs. low)

Subgroup analyses will use the Z-test on event rates (proportions) and also present confidence intervals for the pairwise differences in proportions.

Risk factor analysis using a logistic regression model

To investigate prognostic variables that might have an impact on the primary efficacy endpoint, a logistic regression analysis will be performed to identify potential risk factors. For this analysis, the same variables to define the above subgroups as well as the interaction between treatment and CNI and the interaction between treatment and region will be used. In the model, recipient and donor age, cold ischemia time, and potentially HLA mismatches will be treated as continuous variables.

Analyses with other imputations for missing eGFR (MDRD4) at Month 12

In addition to the imputation method described in Section 9.4.3, the following imputation method will be used to impute missing 12-month eGFR value to define the primary variable – composite endpoint of tBPAR or eGFR (MDRD4) < 50 mL/min/1.73m². With these imputations, non-inferiority and superiority analyses described in Section 9.4.2 will be repeated.

- Subjects who lost their grafts will be assigned a value of zero for their 12-month eGFR;
- Otherwise, subject who had missing value including those who died with a functioning graft will have a 12-month eGFR imputed using the following imputation methods:

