### 2.2.1 Subgroup of Interest

The following demographic/baseline characteristics are defined at the study level as subgroups for specified analyses:

- Recipient characteristics:
  - Age group: <60 vs ≥60 yr
  - Gender
  - Race: Caucasian, Black, Asian and All other races
  - Region: US, EU, Asia, Australia, Latin America, and Middle East

- DGF (delayed graft function)
- BMI <30 and  $\geq 30$
- Donor/transplant characteristics:
  - Age group: <60 vs  $\geq 60$  yr
  - Gender
  - Cold ischemia time: < 20 vs  $\geq 20$  hr
  - End stage disease leading to transplant (Glomerular disease, Diabetes mellitus and All other diseases)
  - Donor type (living donor, standard criteria and expanded criteria deceased donor): donor type will be derived based on Kidney Donor Background Information eCRF, and not the randomization stratification from IRT.
  - HLA mismatches:  $\leq 3$  vs  $> 3$
- CNI (tacrolimus vs. cyclosporine)
- Induction (basiliximab vs. rATG):
  - Basiliximab: preferred term: BASILIXIMAB; drug code/ID: 10892631
  - rATG: preferred term: ANTITHYMOCYTE IMMUNOGLOBULIN, or ANTITHYMOCYTE IMMUNOGLOBULIN (RABBIT); drug code/ID: 10878131 or 10878151

As early use of rATG can be for delayed graft function, type of induction will be identified as the first intake of rATG or basiliximab by Day 1 post-transplant.

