### 2.5.4.3 Subgroup Analysis

Subgroup analyses will be done for the primary composite endpoint of tBPAR or eGFR (MDRD4) < 50 mL/min/1.73m^2 at 12 months for the subgroups defined in [Section 2.2.1](#). Subgroup analyses will use similar methods described in [Section 2.5.2.1](#).

### 2.5.4.4 Analyses with Other Imputations for Missing eGFR (MDRD4) at Month 12

In addition to the main imputation, additional imputation method assuming missing not at random (MNAR) as provided in [Section 4.2.1.2](#) will be used to impute missing 12-month eGFR value to define the primary variable – composite endpoint of tBPAR or eGFR (MDRD4) < 50 mL/min/1.73m^2. With these imputations, non-inferiority and superiority analyses described in [Section 2.5.2](#) will be repeated.

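### The primary composite is tested separately in each of 36 subgroup levels, but for 12 of the 14 factors nothing tests whether the treatment effect differs, and the results are not labelled exploratory

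*Protocol*

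**What the plan says.** Protocol 2.2 sets the objective, the incidence of the primary composite "at Month 12 by subgroup (see Section 9.4.4"). Protocol 9.4.4 gives the method: "Subgroup analyses will use the Z-test on event rates (proportions) and also present confidence intervals for the pairwise differences in proportions". SAP 2.5.4.3 replaces the detail with a pointer: "Subgroup analyses will use similar methods described in" Section 2.5.2.1. That section covers the multiple imputation, the pooling by Rubin's rules that produces a CI and p-value, and the reading of the upper limit against the 10% margin.

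The subgroup factors and their levels are set out in SAP 2.2.1. The list in Protocol 9.4.4 differs: it adds immunological risk, omits DGF and BMI, and gives no levels for race, region or end-stage disease. The count of 36 can therefore be made only from the SAP.

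Effect modification appears in one place for this endpoint in the SAP, the logistic model in 2.5.2 that decides whether the two CNIs are pooled. It contains treatment-by-CNI, tested at 0.10, and treatment-by-region, with no stated decision level. Donor type, HLA mismatch, induction, recipient gender, recipient age, donor age and DGF enter as main effects only. Race, BMI, donor gender, cold ischemia time and end-stage disease are not in the model.

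**The concern.** Whether the regimen performs differently in, say, expanded-criteria recipients is a question about the difference between levels. A p-value or CI inside one level does not answer it. At a common event rate, the result within a level depends largely on how many patients the level holds.

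Two errors follow. Some levels will look positive or harmful by chance. When a real and uniform effect exists, smaller levels will look as if they lack it. For 12 factors the plan contains no analysis that would tell the reader that such a pattern is noise, and no statement that would stop it being read as a finding.

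**Working it through.** **The plan's own power figures.** Inputs from Protocol 9.7: 1020 per arm, 50% event rate, 10-point margin, one-sided 0.025. Non-inferiority power = Φ(0.10/√(0.5/n) − 1.96). This gives 99.5% at n = 1020, 98.1% at 816 and 95.1% at 653, against >99, 98 and 95 in Table 9-1. Superiority at 1020 per arm with a continuity correction gives 60.1, 76.2, 87.9 and 94.8% for 5 to 8 points, against 60, 76, 87 and 94. The same inputs are used below.

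**Counting levels (SAP 2.2.1).**
- "Race: Caucasian, Black, Asian and All other races": 4
- "Region: US, EU, Asia, Australia, Latin America, and Middle East": 6
- "End stage disease leading to transplant (Glomerular disease, Diabetes mellitus and All other diseases"): 3
- "Donor type (living donor, standard criteria and expanded criteria deceased donor"): 3
- Ten two-level factors (recipient age, recipient gender, "DGF (delayed graft function"), BMI, donor age, donor gender, cold ischemia time, HLA mismatch, CNI, induction): 20

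Total 4 + 6 + 3 + 3 + 20 = 36 levels in 14 factors. Without CNI (2) and region (6), 28 levels in 12 factors remain.

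**False significant levels when there is no effect.** No alpha is stated for subgroups, so two-sided 0.05 is assumed. Expected number: 36 × 0.05 = 1.8. If the levels were independent, the chance of at least one would be 1 − 0.95^36 = 84%. They are not independent, because every patient sits in one level of all 14 factors. A simulation therefore placed 2040 patients, randomized 1:1 with a 50% event rate in both arms, into all 14 factors and used an unpooled Wald CI per level (3000 runs per row, complete data). The documents do not give level shares. Equal shares and skewed shares (for example CNI 80/20, living donor 50%) were assumed, with factors independent or correlated at 0.4.

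| Assumed shares, correlation | At least one CI excludes 0 | At least one falsely favours everolimus | At least one of 12 interaction tests p<0.05 |
|---|---|---|---|
| Equal, 0 | 65% | 36% | 44% |
| Equal, 0.4 | 63% | 35% | 41% |
| Skewed, 0 | 69% | 39% | 46% |
| Skewed, 0.4 | 67% | 36% | 44% |

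The last column agrees with 1 − 0.95^12 = 46%.

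**A uniform true benefit of 7 points.** In the same simulation with independent factors, an average of only 16.5 (skewed shares) to 18.1 (equal shares) of the 36 levels reach p<0.05. At least one level has its sign reversed in 56% (equal) to 85% (skewed) of trials, although the effect is identical everywhere.

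**If the 10% margin were also read within levels.** By the formula above, with truly equal arms, power is 29% at 100 per arm, 52% at 200 and 69% at 300. Some bounds need no assumed shares, only an even arm split within levels:
- Living donors make up at least half the population (Protocol 3.1), so the smaller deceased-donor level has at most 1020 × 0.5 / 2 = 255 per arm, giving power of at most 62%.
- The smallest of six regions has at most 1020 / 6 = 170 per arm, giving at most 45%.

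In the simulation, 99 to 100% of null trials had at least one level with an upper limit of 10 points or more.

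**The case against.** The strongest reply is that these analyses are supportive. Protocol 9.4.4 labels them so, and the confirmatory hierarchy has three hypotheses, none of them a subgroup. The one subgroup with a consequence, tacrolimus becoming primary, is triggered by an interaction test. The objective itself speaks of incidence by group and can be read as descriptive. All of this stands, and it limits the point to an improvement in analysis and reporting. It does not remove the gap: tests inside levels are still planned, and supportive is not the same as exploratory.

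Three stronger readings are tempting and should not be made.
- A reader might infer that a false significant subgroup is near certain. The figure is about two in three. Near certainty applies only to at least one level missing the 10% margin.
- A reader might infer that each level will be held to that margin. That is one reading of the SAP pointer, not a stated rule. SAP 2.5.4.4 says expressly that the non-inferiority and superiority analyses are repeated under other imputations; the subgroup section does not. Protocol 9.4.4 mentions no margin for subgroups.
- A reader might multiply 36 levels by four endpoints to reach 144 tests. SAP 2.6.4, 2.7.2.1 and 2.7.2.2 say only that the key secondary endpoint, eGFR below 50 and tBPAR are summarized by subgroup.

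It is also fair that, for a two-level factor, a reader could approximate the between-level contrast from the two reported CIs. That is a reason to report it properly.

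**Conclusion.** The point holds as a modest and cheap improvement. The plan tests within 36 levels and, for 12 of 14 factors, omits the analysis that addresses heterogeneity. It also carries no exploratory label. Under no effect, the chance of at least one falsely significant level is about 63 to 69%, with about 1.8 such levels expected. The range rests on assumed level shares, two-sided 0.05, a 50% event rate and complete data. The margin figures are conditional on the margin being applied within levels, which the documents leave unclear. No confirmatory claim of the trial is affected.

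**What to change.** Amend SAP 2.5.4.3 as follows.

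1. For each factor, in each of the 100 imputed datasets, compute the difference between levels in the treatment risk difference. Pool by Rubin's rules and report it with a 95% CI and one heterogeneity p-value. Factors with more than two levels need a joint test of the contrasts.
2. Keep level-specific rates, differences and CIs as a descriptive forest plot, and drop the within-level p-values.
3. State that subgroup results are exploratory.
4. State that the 10% margin and the superiority rule apply only to the prespecified hierarchy, including its tacrolimus contingency.

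The cost is SAP wording and a few lines of code on the imputed datasets of SAP 4.2.1.1 and the risk-difference output of SAP 4.7.1. No new data or design change is needed.

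The downside is low power. For an even split (510 per arm per level, 50% event rate) the standard error of the contrast is √(0.5/510 + 0.5/510) = 4.4 points, twice the overall √(0.5/1020) = 2.2 points, so the 95% CI is about ±8.7 points. For an 80/20 split it is 1.96 × √(0.5/816 + 0.5/204) = ±10.8 points. The CI should therefore be read ahead of the p-value. Twelve such tests at 0.05 still give roughly a 41 to 46% chance of at least one false signal, which is why item 3 is part of the fix.

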For the composite efficacy failure (tBPAR, graft loss or death) at Month 24 and the composite endpoint of BPAR, graft loss or death at Month 12 and Month 24, Kaplan-Meier event rates will be estimated and compared between the everolimus plus reduced CNI and the MPA plus standard CNI arm. Similarly Kaplan-Meier event rates will be estimated and compared for AR, tAR, BPAR, tBPAR, humoral rejection, graft loss, death and the composite endpoint of graft loss or death. To assess time-to-event occurrence of efficacy endpoints, Kaplan-Meier plots will be produced and the log-rank test will be performed. A forest plot of KM event rate differences for efficacy endpoints will be produced. Severity of tBPAR will be tabulated by treatment.

As a key component of the primary endpoint (tBPAR or eGFR (MDRD4) < 50 mL/min/1.73 m²), the endpoint of eGFR (MDRD4) < 50 mL/min/1.73m² will be summarized with raw incidence rates and compared. A Z-test based 95% confidence interval will be provided.

For eGFR(MDRD4) at Month 12 and Month 24, analysis of covariance (ANCOVA) will be performed with treatment (everolimus vs MPA), CNI (CsA vs TAC), interaction of treatment and CNI, region, interaction of treatment and region, induction, donor type (living donor, deceased standard criteria donor and deceased expanded criteria donor), recipient gender and donor gender as factors, and recipient age and BMI, donor age, cold ischemic time and eGFR(MDRD4) at Month 1 as covariates. The missing Month 12 or Month 24 values will be imputed using the same methods as described in Section 9.4.3 and Section 9.4.4 except LOCF approach for Month 24, for which a Month 24 eGFR value will be imputed using the last nonmissing observation carried forward (LOCF) from Month 6 onwards as subjects will be maintained in the same CNI target range since Month 6.

Renal function and change from Month 1 (Week 4) will be summarized by visit with descriptive statistics and graphically presented by visit.

The evolution of renal function (eGFR by MDRD4) will be evaluated via a mixed effect model with intercept and subject as random effects and using with the same covariates/factors as used for the ANCOVA model. Based on the mixed effect model, the treatment groups will be compared, and slope of renal function evolution for each treatment group will be assessed.

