### 2.1 Data Analysis General Information

The cut-off day is defined as the latest study day before and up to which data will be used in the analysis on an individual patient level. The cut-off date for 12-month analysis will be the day of Month 12 Visit (specifically, Date of Discontinuation/Study Phase Completion as recorded on the Month 12 Disposition eCRF) + 2 Weeks, but no later than Day 450 (upper limit of Month 12 analysis window). For the 24-month analysis, there will be no cut-off day. All data in the clinical database will be used for the analyses.

Data listings will include all data collected up to the cut-off date for the 12-month analysis, or all data recorded in the database for the 24-month analysis.

For summary tables and figures, the following rules will be applied unless otherwise indicated:

- Categorical data will be summarized by frequencies and percentages. Continuous data will be summarized by mean, median, standard deviation, minimum and maximum and the number of non-missing data points.
- All AE/Infection, notable events, CMV information, EBV information and other events of interest will be summarized based on all collected events with onset on or after the first day of study medication up to the cut-off date or seven days after last dose of study medication. For SAE/infection and death, all events will be summarized.
- All lab or vital sign tables will include data up to the cut-off date or two days after last dose of study medication (on-treatment analysis);

- Efficacy and renal function analyses will be primarily based on all available data including those after study medication discontinuation; as a sensitivity analysis they will include only data up to two days after last dose of study medication (on-treatment analysis). Patients will be censored for the time to event analyses if they do not have an event. For on-treatment analysis, the censoring day is two days after discontinuation of study medication or the last contact day, whichever is earlier; for analysis regardless of on-treatment or off-treatment, the censoring day is the last contact day.
- For post-baseline continuous values, for a given patient, if multiple numeric measurements for a given variable are reported within the same visit window (see the definition for visit windows in [Section 4.1](#)), the following rule will be applied:

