### 2.1.1.3 Last Contact Day

The last contact day for the 12-month analyses will be determined by screening the 12-month database and taking the maximum of any dates found post-randomization. If the maximum date is after the cut-off date for the 12-month analysis, use the cut-off day as the last contact day for the 12-month analysis.

The last contact day for the 24 months analyses corresponds to the last recorded date in the database (across all visit dates itself, all visit related assessment dates, other assessment dates, event dates (start and end), medication dates). It should be prior to or on the day of study completion and therefore dates of events which occur after study completion will not be considered.

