### 2.7.2.2 Endpoints without eGFR (MDRD4) < 50 mL/min/1.73m^2 as a Component

Based on FAS, for the composite efficacy failure (tBPAR, graft loss or death) at Month 24 and the composite endpoint of BPAR, graft loss or death at Month 12 and Month 24, Kaplan-Meier event rates will be estimated and compared between the everolimus plus reduced CNI and the MPA plus standard CNI arm. Similarly Kaplan-Meier event rates will be estimated and compared for AR, tAR, BPAR, tBPAR, tBPAR excluding grade IA rejections, AMR, graft loss, death, the composite endpoint of graft loss or death, and composite endpoint of tBPAR, graft loss, death, or loss to follow-up at Months 12 and 24. Kaplan-Meier event rate difference, 95% confidence interval and p-value for equality test will be provided. To assess time-to-event occurrence, Kaplan-Meier tables and plots will be produced with a log-rank test p-value for the above variables.

In addition, severity of tBPAR will be tabulated by treatment. The endpoint of tBPAR at Month 12 will be summarized on the FAS for the subgroups defined in [Section 2.2.1](#)

Forest plots of event rate differences for **all** efficacy endpoints specified in [Section 2.7.2](#) will be produced on the FAS.

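### Kaplan-Meier rates for rejection and graft loss slightly overstate the incidence the objective asks for, because death and graft loss are handled as ordinary censoring

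*Protocol*

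**What the plan says.** The objective in Protocol 2.2 is "The incidence of individual endpoints of death, graft loss, tBPAR, BPAR, tAR, AR and humoral rejection at Months 12 and 24". It names no estimator.

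The estimator comes later. Protocol 9.5.2 states: "Similarly Kaplan-Meier event rates will be estimated and compared for AR, tAR, BPAR, tBPAR, humoral rejection, graft loss, death". SAP 2.7.2.2 repeats this on the full analysis set with one endpoint added: "Similarly Kaplan-Meier event rates will be estimated and compared for AR, tAR, BPAR, tBPAR, tBPAR excluding grade IA rejections, AMR, graft loss, death". On output, the SAP says "Kaplan-Meier event rate difference, 95% confidence interval and p-value for equality test will be provided", and adds log-rank tests and forest plots.

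The censoring rule is general. SAP 2.1 states "Patients will be censored for the time to event analyses if they do not have an event", and "for analysis regardless of on-treatment or off-treatment, the censoring day is the last contact day". SAP 2.1.1.3 finds the last contact day for the 12-month analysis by "taking the maximum of any dates found post-randomization", capped at the cut-off. For the 24-month analysis it is the last recorded date, and events after study completion are not considered.

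Protocol 5.5.9 and 6.4 list graft loss as a reason for discontinuation from the study. Neither document mentions competing risks or a cumulative incidence function.

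**The concern.** One minus Kaplan-Meier estimates the proportion who have an event only if censored patients could still have it at the same rate as those who remain. That fails for two groups here. A patient who has died can neither reject nor lose the graft, and a graft already lost cannot later be rejected. When such patients are censored, the estimator redistributes their future risk to the survivors. The result is the risk in a setting where nobody dies or loses a graft first, which is not the incidence named in the objective. The direction is fixed: the Kaplan-Meier rate is always at or above the cumulative incidence.

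Readers will use these component rates to judge how often rejection and graft loss occurred on reduced calcineurin inhibitor exposure. At stake is the accuracy of those absolute figures.

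**Working it through.** **Which patients are affected.** A patient who dies without the event has a last contact day that is in effect the date of death, so death censors. For rejection endpoints, graft loss ends study participation, so follow-up is censored at or soon after it. This follows from the general rule; it is not written out for these endpoints. Death alone has no competing event, and composites that count both death and graft loss as events are free of the problem.

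**Size.** The plan states no expected rate of rejection, graft loss or death, so there is no figure to reproduce and every rate below is an assumption. The one input from the documents is timing: SAP 2.12.1 cites an earlier study with 80% of tBPAR events in the first 6 months. I apply this as 80% of the 12-month cumulative hazard.

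With h the rejection hazard and c the competing hazard accumulated in an interval, and S the probability of being free of both at its start:

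- One minus Kaplan-Meier = 1 − exp(−Σh)
- Cumulative incidence = Σ S × h/(h + c) × (1 − exp(−(h + c)))

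*Worked example.* Net rejection is 10% at Month 12, with a further hazard of 0.02 to Month 24. Death or graft loss is 5% by Month 12 and 8% by Month 24, with half of the 12-month competing hazard before Month 6. The 12-month rejection hazard is −ln(0.90) = 0.10536, split 0.08429 and 0.02107. The competing hazard is −ln(0.95) = 0.05129, split into two parts of 0.02565, then −ln(0.92) − 0.05129 = 0.03209.

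| Interval | S | h | c | Increment |
|---|---|---|---|---|
| 0–6 months | 1.0000 | 0.08429 | 0.02565 | 7.98% |
| 6–12 months | 0.8959 | 0.02107 | 0.02565 | 1.84% |
| 12–24 months | 0.8550 | 0.02000 | 0.03209 | 1.67% |

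- Month 12: 10.00% against 9.83%, an excess of 0.17 points.
- Month 24: 11.78% against 11.49%, an excess of 0.29 points.

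With 80% of the 12-month competing hazard before Month 6, the excess is 0.25 and 0.36. With competing events of only 2% and 3%, it is 0.07 to 0.10 at Month 12 and 0.11 to 0.14 at Month 24.

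*Other assumed rates.* These take graft loss and death separately, with deaths uniform over time. Entries are the excess for tBPAR in points, Month 12 / Month 24.

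| tBPAR M12/M24 | Graft loss, death by M24 | Half of graft losses in first 30 days | Graft losses evenly spread |
|---|---|---|---|
| 10% / 12% | 4%, 3% | 0.27 / 0.38 | 0.12 / 0.22 |
| 12% / 15% | 6%, 5% | 0.49 / 0.75 | 0.23 / 0.47 |
| 15% / 20% | 8%, 8% | 0.85 / 1.48 | 0.42 / 1.00 |

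*Graft loss, with death competing.* With net graft loss of 2 to 5% at Month 12 and death of 1 to 5% and 2 to 8% at Months 12 and 24, the excess is 0.01 to 0.13 points at Month 12 and 0.02 to 0.19 at Month 24. With 8% graft loss evenly spread and 8% death by Month 24, it reaches 0.32.

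**Arm differences.** With 10% net rejection in both arms and competing events of 4% against 6% at Month 12 and 6% against 9% at Month 24, the two estimators' arm differences part by about 0.08 and 0.12 points. A wider imbalance (graft loss 4% against 7%, death 3% against 5% by Month 24, rejection 12%/15%, early graft loss) gives about 0.23 and 0.35. For scale, the 95% CI half-width with 1020 per arm is 1.96 × √(2p(1 − p)/1020): 2.6 points at p = 10% and 2.8 at p = 12%.

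**The case against.** A reader might infer that an imbalance in deaths or graft losses would distort the Kaplan-Meier comparison of rejection between arms. The reverse holds. With independent cause-specific hazards, 1 − exp(−Σh) does not involve the competing events. Take the same rejection hazard in both arms (10% and 12% at Months 12 and 24), with graft loss 3% against 5% and death 3% against 4% by Month 24, and half of graft losses in the first 30 days. Kaplan-Meier gives 10.00% and 12.00% in both arms, a difference of zero. Cumulative incidence gives 9.79% against 9.66%, and 11.69% against 11.52%. The arm with more deaths and graft losses looks slightly better on rejection only under cumulative incidence. For the question of whether a regimen changes the rate of rejection, the planned Kaplan-Meier and log-rank comparison is therefore defensible and should stay.

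Three further objections have some force:

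- SAP 4.3.10 refers to simple proportion tables for each endpoint. With complete follow-up the crude proportion equals the Aalen-Johansen estimate, so an approximate absolute-risk display is anticipated. But SAP 2.7.2.2 makes Kaplan-Meier the estimate that is compared and given a confidence interval.
- Censoring at graft loss is inferred. SAP 2.1 censors at last contact, and SAP 4.2.1.1 speaks of visits on and after graft loss. Any patient followed beyond graft loss stays in the risk set, which brings Kaplan-Meier closer to the cumulative incidence. The calculations assume that follow-up stops at once, so for rejection they lean high.
- The size depends on chosen rates and timing. Early graft loss in particular is not documented, and it raises the figure.

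**Conclusion.** The point stands as a mismatch between the stated objective and the planned estimator, with a known direction and a modest size. Under moderate assumed rates, Kaplan-Meier overstates rejection incidence by roughly 0.1 to 0.5 points. It reaches 0.75 at Month 24 in the middle scenario with early graft loss, and about 1 to 1.5 by Month 24 in the scenario with 20% rejection and 8% each of graft loss and death. For graft loss the excess is about 0.3 points or less. All of these rest on assumed rates, independent hazards and immediate censoring at graft loss.

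The documents do not support reading this as a threat to the trial's confirmatory conclusions. The primary endpoint is a binary proportion with multiple imputation, and the key secondary endpoint counts graft loss and death as events. The affected outputs are other secondary endpoints outside the testing hierarchy. The effect on arm differences is small beside their confidence intervals. What needs correcting is the label and estimator of the absolute incidence, not the comparison of rejection hazards.

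**What to change.** In SAP 2.7.2.2, report Aalen-Johansen cumulative incidence at Months 12 and 24, with the arm difference and its 95% CI, as the incidence estimate for:

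- AR, tAR, BPAR, tBPAR, tBPAR excluding grade IA, and AMR, with death and graft loss as competing events;
- graft loss, with death as the competing event.

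Keep the planned Kaplan-Meier rates and log-rank tests beside these, labelled as net (cause-specific) estimates. They remain the appropriate comparison of rejection hazard and allow comparison with earlier trials. Leave Kaplan-Meier unchanged for death and for composites containing both death and graft loss.

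The cost is SAP wording and an event-code option in the survival procedure. The dates of death and graft loss are already collected, so no new data are needed. The downside is one more set of estimates to present, and headline rates slightly lower than those of earlier trials that used Kaplan-Meier.
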